Enhancing Older Adult's Everyday Memory Function

Study Protocol

NCT #: NCT04088136

12/07/2022

RCT PROTOCOL

Project Overview

The Everyday Memory and Metacognitive Intervention (EMMI) is assessed in comparison to an Active Control group (MSC). Participants are randomly assigned to either the EMMI group or MSC group. All participants, regardless of being assigned to the EMMI group versus MSC group, follow the same procedure (outlined below). The only difference between the two groups is the type of memory training the participants receive, which corresponds to the type of shaping calls they receive and the evening surveys they complete.

The intervention was administered in small groups of 3-6 persons all from the same intervention arm (MSC or EMMI). There were four group learning experiences (GLEs), 2 per week for 2 weeks. Individuals viewed PowerPoint presentations given by the interventionist and assistants. These sessions lasted 3 hours and emphasized interaction and group discussion of key points, as well opportunities for participants to share with each other ideas or insights they gained through working on in-class exercises. Participants also completed assigned homework tasks practicing trained skills between each session. Homework was discussed in the next GLE, but was also reviewed in one-on-one shaping calls, in which a member of the team contacted each participant to discuss how they were working with and using the trained techniques, with specific reference to homework exercises.

A key measurement method for the study was using smartphone apps on burner Samsung Galaxy phones that were locked down so as to enable use of the phone only for the research study. Individuals reported on everyday memory experiences via event-based memory problem reporting and an end-of-day diary that recorded reports of memory failures that had occurred that day. The training program for participants required extensive technical support in how to use these burner phones for ecological momentary assessment (EMA).

7-Week Schedule for Each Group of Participants

Task	Week 1	Week 2	Week 3	Week 4	Week 5	Week 6	Week 7
Screening	X						
Informed Consent	X						
Random Assignment	X						
Intake Interview	X						
Pre-Test Sessions		X					
Phone Shipment/Delivery			X				
GLE with Shaping Calls			X	X			
EMA with Shaping Calls					X		
EMA without Shaping Calls						X	
Prospective Memory Call-in Task						X	X
Post-Test Sessions							X
Debrief							X

Waiver of Informed Consent + Telephone Screening for Study Eligibility

1. WAIVER: Before screening, research team member will obtain telephone consent.
2. SCREENING: After telephone consent is obtained, administer the Telephone Interview for Cognitive Status (TICS). A TICS score of 31 or above is required to participate in the study.
3. Email the participant the consent form via DocuSign.

Intake Interview

1. INTERVIEW: After we receive the informed consent form in DocuSign, participants will be scheduled for their 1-hour intake interview, held on Zoom. All notes collected during the interviews will be entered into a Qualtrics form.

Pre-Test

1. Pre-Test Session #1 (Online):
 - a. Demographic Questionnaire
 - b. Technology Questionnaires
 - c. COVID-19 Questionnaire
 - d. Leisure Activity Scale
 - e. Letter Sets Test
 - f. Personal Beliefs about Memory
 - g. Global Beliefs about Memory
 - h. Word List Free Recall
2. Pre-Test Session #2 (Online):
 - a. Shipley Vocabulary
 - b. Perceived Stress Scale
 - c. Satisfaction with Life Scale
 - d. Memory Functioning Questionnaire
 - e. Memory Compensation Questionnaire
 - f. Personality Questionnaire
 - g. Pattern Comparison
 - h. Verbal Paired Associates

Group Learning Experience + Shaping Calls #1, #2, #3

1. The “Group Learning Experience” (GLE) includes the memory classes. These classes involve a small group of participants (3-6 people) who meet with the trainer to learn the memory strategies.
2. The EMMI and MSC GLEs include four classes (either Mondays/Thursdays or Tuesdays/Fridays) across the span of two weeks. Shaping calls will occur during both weeks of the GLE, plus the week following the conclusion of the GLE.
3. EMMI GLE:
 - o GLE Day 1
 - i. Topics:
 1. Beliefs About Memory
 2. Intentional Encoding
 3. Spaced Retrieval
 - ii. In-Class Activities: N/A

- iii. Homework:
 - 1. HW #1: Belief Restructuring
 - 2. HW #2: New Name Learning
- o GLE Day 2
 - i. Topics:
 - 1. Goal setting and how to do it
 - 2. External Aids
 - 3. Stop Think Plan Act
 - ii. In-Class Activities:
 - 1. Spaced Retrieval
 - 2. Routines and Habits
 - iii. Homework:
 - 1. HW #3: Daily Goal Setting
 - 2. HW #4: External Aids
 - 3. HW #5: Stop/Think/Plan/Act
- o GLE Day 3
 - i. Topics:
 - 1. Implementation Intentions
 - 2. Medications
 - 3. Habits and Routines
 - ii. In-Class Activities:
 - 1. Implementation Intentions
 - iii. Homework:
 - 1. HW #6: Medication Intentions
 - 2. HW #7: Routines and Habits
 - iv. Provide Prospective Memory Call-in Task Instructions
- o GLE Day 4
 - i. Topics:
 - 1. Smartphone Training
 - 2. Review next steps in study
 - ii. In-Class Activities: N/A
 - iii. Homework: Submit practice Memory Blip Survey

4. MSC GLE:

- o GLE Day 1
 - i. Topics:
 - 1. Beliefs About Memory
 - 2. Intentional Encoding
 - 3. Organizational Strategies
 - ii. In-Class Activities:
 - 1. Categorizable Free Recall Task Version #1
 - iii. Homework:
 - 1. HW #1: Belief Restructuring
 - 2. HW #2: Categorizable Free Recall Task Version #2
- o GLE Day 2
 - i. Topics:
 - 1. Organizational Encoding
 - 2. Associative Encoding/Mediation strategies
 - ii. In-Class Activities: N/A
 - iii. Homework:

- 1. HW #3: Serial Free Recall
- 2. HW #4: Paired Associates
- o GLE Day 3
 - i. Topics:
 - 1. Associative Encoding
 - 2. Self-Testing
 - ii. In-Class Activities:
 - 1. Create paired associates flashcards
 - iii. Homework:
 - 1. HW #5: Self-Testing
 - iv. Provide Prospective Memory Call-in Task Instructions
- o GLE Day 4
 - i. Topics:
 - 1. Distinctiveness
 - 2. Smartphone Training
 - 3. Review next steps in study
 - ii. In-Class Activities:
 - 1. Paired Associates Homework #5 (same word pairs studied during GLE Day 3):
 - iii. Homework: Submit practice Memory Blip Survey
- 5. SHAPING CALLS DURING GLE WEEKS 1 and 2:
 - o WEEK 1: Two shaping calls are held during GLE Week 1 (one call the day after each GLE). During these calls, check-in on homework and ask the participant if they have any questions.
 - o WEEK 2: One shaping call during GLE Week 2 (one call after GLE Day 3). During the call, check-in on homework and questions.
- 6. PROSPECTIVE MEMORY (PM) CALL-IN TASK:
 - o During GLE Day 3 (for both groups), participants are instructed to call the lab two times in Week 6 and two times in Week 7. This task is an assessment of prospective memory. PM Calls should not be scheduled during the participant's Post-Test sessions in Week 7.

16-Day Measurement Period + Shaping Calls #4, #5, #6

1. The day after GLE Day 4, participants will begin the 16-day measurement period. Every day for 16 consecutive days, participants will complete the Morning Survey, Evening Survey (i.e., nightly diary), and blip reports in the Memory Blip Survey (event-based ecological momentary assessment app).
2. MEASUREMENT PERIOD WEEK 1: Participants will receive three additional shaping calls from the lab after the conclusion of the GLE. The sixth call is a check-in to let the participants know the research team will not call them again, but that they can call us if questions/problems come up. Before holding shaping calls #4, #5, and #6, the research team member should review the memory blips submitted by each participant.
3. MEASUREMENT PERIOD WEEK 2: Participants will not receive shaping calls during the second measurement period week.

Prospective Memory Call-in Task

1. Participants are asked to complete four Prospective Memory (PM) calls during Weeks 6 and 7. PM calls are typically scheduled on Monday/Wednesday and Tuesday/Friday in Weeks 6 and 7, respectively. No PM calls are scheduled over the weekends. Typically, calls are scheduled between 9:00am – 6:00pm.

Participants will be given instructions for this task during GLE Day 3. Participants may reschedule any PM calls that conflict with their schedule on or before GLE Day 4.

2. PM contacts will either be made via phone call, text, or email.

Post-Test

1. Post-Test Session #1 (Online):
 - a. COVID-19 Questionnaire
 - b. Personal Beliefs about Memory
 - c. Global Beliefs about Memory
 - d. Simulated Everyday Memory: Prescription Refill
 - e. Simulated Everyday Memory: Banking
 - f. Verbal Paired Associates
2. Post-Test Session #2 (Online):
 - a. Story Recall
 - b. Perceived Stress Scale
 - c. Satisfaction with Life Scale
 - d. Memory Functioning Questionnaire
 - e. Memory Compensation Questionnaire
 - f. Word List Free Recall

Debrief & Participant Compensation

1. After the participant completes Post-Test Session #2, call the participant and read the debriefing statement.
2. Payment issued by check.

Re-Design to Accommodate COVID-19

The original study proposal envisaged group learning sessions to take place on the campus of Georgia Tech, as was done with our original intervention study (Pearman et al., 2020). The pandemic forced us to convert to completely remote assessment, which also required providing technical support to participants in using web-based platforms. All questionnaires, surveys, and cognitive tests were administered via Qualtrics forms, except the proprietary iFunction programs used to simulate everyday complex IADLs. Programs had to be modified to account for computing power and bandwidth issues for some participants, identified in pilot data. Some (but relatively little) data were lost through lost internet connections, program crashes, etc.

Enhancing Older Adult's Everyday Memory Function

Statistical Analysis Plan

NCT #: NCT04088136

12/07/2022

## Statistical Analysis Plan: Study 2

Participants will be randomly assigned to one of two intervention arms: Everyday Memory Metacognitive Intervention (EMMI) and Memory Strategy Control (MSC). The EMMI group is trained in everyday memory skills applicable to self-management of cognitive challenges; the MSC group is trained in mnemonic strategies to form new memories for subsequent memory tests. We are planning to enroll 30 persons in each of the two intervention arms (total N = 60).

We have designated selected primary and secondary outcomes to evaluate. The hypotheses are that (1) EMMI training will improve everyday memory, but not typical memory test performance; and (2) MSC training will improve typical memory test performance but not everyday memory. These hypotheses translate into directional null and alternative hypotheses in standard frequentist statistics. Outcomes are differentiated by whether they are administered at both pretest and posttest or at posttest only. For everyday memory, the posttest-only outcomes include (1) everyday memory failures, or memory slips; (2) laboratory contact task to measure prospective memory, with (a) number of successful calls and (b) timeliness relative to scheduled contact time; and (3) computer simulated tasks assessing complex IADLs, including ATM use and medication management. We predict better performance by the EMMI group at posttest on these measures. The posttest-only cognitive measure is Story Recall, which is seen as a transfer task unlikely to show training benefits, but the directional hypothesis is for better performance in the MSC group.

We estimate the design has a .80 statistical power to detect a standardized mean difference favoring the EMMI group of  $d = 0.64$ ,  $\alpha = .05$ , 1-tailed.

For outcomes measured at pretest and posttest, we administered several metamemory questionnaires, and designated the following key secondary outcomes: change on MFQ Frequency of Forgetting (a measure of everyday memory complaints), change in PBMI Specific Memory Self-Efficacy and Perceived Control over Memory scales, and change in the Memory Compensation Questionnaire's scales of External Use and Internal Use, assessing use of strategies to support everyday memory. For these measures we hypothesized that the EMMI group would improve in subjective memory more than the MSC group from pretest to posttest. We also administered two memory tests at pretest and posttest, an associative recall test and a free recall test. We hypothesized greater improvement from pretest to posttest for the MSC group who received training in relevant mnemonic strategies that should benefit level of remembering.

Posttest-only analyses will be conducted as independent samples t-tests on key measures with a one-tailed test, according to the direction of the relevant hypotheses. Pretest-Posttest data will be analyzed using Group X Time mixed effects models using SAS PROC MIXED, with repeated measures specified for Time (pretest-posttest).

We also predict that the everyday memory intervention will reduce memory complaints and increase memory self-efficacy and perceived control from pretest to posttest in the EMMI group alone, leading to the prediction of a group (MSC vs. EMMI) X time (pretest, posttest) interaction. Conversely, we predict that memory strategy training in the MSC group will improve memory test performance, leading to the prediction of a group (MSC vs. EMMI) X time (pretest, posttest) interaction. The interaction is a direct analog of a 1 *df* planned comparison for differential gain for the two groups, and hence is also amenable to a directional hypothesis test, halving the critical p-value used for the typical F-test for interaction. We estimate that the design has .80 power to detect these interactions, assuming a training benefit effect size (difference in  $d$ ) of 0.75, 1 tailed (comparable to pretest-posttest associative mnemonic training gains in our lab).

Given that we have selected critical outcome measures and specified a priori hypotheses, no adjustments of critical p-values will be made, especially because we do not wish to sacrifice statistical power for a conservative control over the Type I error rate.

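### Both main hypotheses say that one training will not improve the other domain, but the planned tests only compare the arms, so these no-effect halves are untested and should be restated as comparisons

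*SAP*

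**What the plan says.** The SAP (Statistical Analysis Plan: Study 2) gives the two hypotheses as "1) EMMI training will improve everyday memory, but not typical memory test performance; and (2) MSC training will improve typical memory test performance but not" memory in everyday life. It then says: "These hypotheses translate into directional null and alternative hypotheses in standard frequentist statistics".

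Two kinds of test follow.

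- For outcomes measured once: "Posttest-only analyses will be conducted as independent samples t-tests on key measures with a one-tailed test, according to the direction of the relevant hypotheses". The everyday-memory outcomes listed here are memory slips, the laboratory contact task and the simulated tasks, with EMMI predicted to do better. Story Recall is the one cognitive measure in this group.
- For outcomes measured twice: "Pretest-Posttest data will be analyzed using Group X Time mixed effects models using SAS PROC MIXED, with repeated measures specified for Time (pretest-posttest"). The quantity tested is the one-degree-of-freedom difference in gain between arms, one-tailed. It covers the associative and free recall tests, where MSC is predicted to gain more, and the questionnaire scales, where EMMI is.

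On Story Recall the SAP says: "The posttest-only cognitive measure is Story Recall, which is seen as a transfer task unlikely to show training benefits". The same sentence goes on to give a directional hypothesis in favour of MSC.

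The sample size is stated as: "We are planning to enroll 30 persons in each of the two intervention arms (total N = 60"). Both power statements are for superiority: a standardized difference of 0.64 for posttest-only outcomes and a difference in gain of 0.75 for the interactions. Neither document specifies an equivalence margin, a confidence bound or a within-arm contrast.

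**The concern.** The null hypothesis of a one-tailed EMMI-versus-MSC test is a statement about the difference between arms. That EMMI does not improve recall, or that MSC does not improve everyday memory, is a statement about one arm's own change. The SAP's step from the second kind of statement to the first leaves half of each hypothesis without a test.

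The risk is that the missing half is assumed from the other arm's win. If MSC beats EMMI on recall, it is easy to write that EMMI did not improve recall, yet both arms may have gained. The curricula in the Protocol make this plausible. Both arms are taught beliefs about memory and intentional encoding and do the belief-restructuring homework. EMMI also practises spaced retrieval and name learning, and MSC practises self-testing. Hypotheses 1 and 2 could then be reported as supported in full when half of each is false.

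**Working it through.** **Inputs.** From the SAP: 30 per arm, one-tailed alpha .05, d = 0.64 for posttest-only outcomes, and a difference in gain of 0.75 for interactions. Assumed here, because the SAP gives no value: pretest-posttest correlation r from .3 to .7, equal unit SDs at both times, no dropout, and (step 5 only) a 0.5 SD margin and a 0.3 SD retest gain.

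**1. The stated power.** Noncentrality = 0.64 / sqrt(2/30) = 2.479 on 58 df. The one-tailed critical value is 1.672 and power is .790 (normal approximation .798). The stated .80 is therefore reproduced, and it is one-tailed superiority power.

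**2. What the interaction responds to.** The SD of change is sqrt(2(1 - r)). Noncentrality = (MSC gain - EMMI gain) / (sqrt(2(1 - r)) x sqrt(2/30)). EMMI's own gain enters only through the difference. For a 0.75 difference:

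| Assumed r | SD of change | Noncentrality | Power |
|---|---|---|---|
| .3 | 1.183 | 2.455 | .783 |
| .5 | 1.000 | 2.905 | .890 |
| .7 | 0.775 | 3.750 | .980 |

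Simulation at r = .5 (100,000 runs per case) confirms this. MSC wins with probability .890, .890 and .889 when EMMI's true gain is 0, 0.3 and 0.5 SD. A significant interaction carries no information on whether EMMI improved.

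**3. Posttest-only everyday outcomes.** The same holds for the t-test. With true gains of 0.64 (EMMI) and 0 (MSC) it rejects in .789 of runs; with 1.14 and 0.5 it rejects in .791. Here no further analysis can help:

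- The Protocol's Pre-Test list contains none of these measures.
- Memory-slip reporting starts the day after GLE Day 4.
- The contact task falls in Weeks 6 and 7.
- Both arms are trained.

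MSC's change on these outcomes is not estimable.

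**4. Story Recall.** The 90% CI half-width for the between-arm difference is 1.672 x sqrt(2/30) = 0.43 SD. Power is .606 at a true difference of 0.5 SD and .455 at 0.4 SD. A non-significant result therefore leaves moderate differences open.

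**5. What a formal no-gain claim for EMMI on recall would take.** Suppose the claim is made when the one-sided 95% upper bound for EMMI's change lies below 0.5 SD. The standard error is sqrt(2(1 - r)/30), with 29 df. The chance of meeting the criterion when the training effect is zero is:

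| Assumed r | Standard error | No retest gain | Retest gain 0.3 SD |
|---|---|---|---|
| .3 | 0.216 | .73 | .23 |
| .5 | 0.183 | .85 | .28 |
| .7 | 0.141 | .96 | .40 |

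Without an untrained arm, retest gain cannot be separated from training gain. The rule is conservative, and its power depends heavily on retest gain.

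**The case against.** The best reply is that the SAP already works comparatively below its summary sentence. It predicts better EMMI performance at posttest and greater MSC gain on the memory tests, and it describes the interaction as a comparison of gains. Read that way, the no-effect wording is shorthand for a relative dissociation, which the directional tests do address. This stands, and it is why rewording is the main remedy. It does not make the literal hypotheses testable, and the SAP uses absolute language again when it predicts subjective-memory benefit in EMMI only.

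Three stronger readings are tempting, and the documents do not support them.

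- **That the plan will read non-significance as no effect.** Neither document says so. On recall the argument would not work either: a non-significant MSC-over-EMMI test means that MSC's predicted advantage was not shown, and it does not support the claim that EMMI fails to improve. The route to guard against is inference from a significant win.
- **That Story Recall is planned as a test of no transfer.** It has a directional hypothesis favouring MSC. The low expectation of benefit is background, so step 4 supports only a caution on interpretation.
- **That no everyday-memory measure has a pretest.** MFQ Frequency of Forgetting, which the SAP describes as a measure of everyday memory complaints, is taken at both times, so MSC's change in complaints can be estimated. The limit applies to the posttest-only outcomes.

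It is also fair to say that any two-arm comparison with an active control depends only on the difference between arms. That is not a defect of the tests; the difficulty lies in hypotheses that ask for more.

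**Conclusion.** The concern holds as a mismatch between the stated hypotheses and the planned tests. The superiority tests are valid for superiority, and their power, error rates and sample size are not in question here. The no-effect half of each main hypothesis is untested. The interaction's rejection probability for a 0.75 SD difference in gain (.78 to .98 for r from .3 to .7) is the same whatever the losing arm gained. For MSC on memory slips, the contact task and the simulated tasks, the claim is beyond the design. For EMMI on the recall tests, the planned model can estimate the change, but the SAP does not ask for it.

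The structural conclusion needs no assumption about r; only the size of the probabilities does. The change should be made, because it decides what the trial may conclude and costs almost nothing.

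**What to change.** 1. Restate the hypotheses to match the tests: (1) EMMI yields better everyday memory than MSC; (2) MSC yields greater gain on memory tests than EMMI.
2. State that no conclusion of no improvement will be drawn for MSC on the posttest-only everyday outcomes, because they have no pretest and the trial has no untrained arm.
3. For the associative and free recall tests, report EMMI's pretest-posttest change with its confidence interval from the same PROC MIXED model. Note that it mixes retest and training gain, and do not claim that EMMI fails to improve from the interaction alone.
4. For Story Recall, report the difference with its confidence interval, and do not treat a non-significant result as evidence of no transfer.
5. Optional: if the sponsor wants a formal no-gain claim for EMMI on recall, it should justify a margin in advance and state the power allowing for retest gain. At the 0.5 SD margin assumed above, that is about 73% to 96% with no retest gain and about 23% to 40% with a 0.3 SD retest gain.

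Items 1 to 4 need SAP wording and one extra estimate from the existing model, with no new data or participants. The cost is a narrower message: the double dissociation becomes a relative one.

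### Posttest-only outcomes are tested without baseline adjustment although suitable scores are already collected: a cheap gain in precision, of uncertain size

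*SAP*

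**What the plan says.** The SAP section for Study 2 separates outcomes measured at pretest and posttest from those measured at posttest only. On the second kind it says: "For everyday memory, the posttest-only outcomes include (1) everyday memory failures, or memory slips". It then adds the laboratory contact task (number of successful calls and timeliness) and the simulated complex IADL tasks. Story Recall is the posttest-only cognitive measure. The test for all of them is given in one sentence: "Posttest-only analyses will be conducted as independent samples t-tests on key measures with a one-tailed test, according to the direction of the relevant hypotheses." No covariate or stratification factor is named. Pretest values enter only the Group X Time models for the other outcomes.

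On power the SAP says: "We estimate the design has a .80 statistical power to detect a standardized mean difference favoring the EMMI group of" 0.64, at one-tailed alpha .05, with 30 people planned per arm.

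Two kinds of earlier score exist for the same participants:

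- **TICS.** The protocol's telephone screening section gives its only stated use: "A TICS score of 31 or above is required to participate in the study." The 7-week schedule lists screening before random assignment, both in Week 1. The order is inferred from the table; no sentence states it.
- **Pretest battery.** It is collected in Week 2, after assignment and before training starts in Week 3. It includes "Word List Free Recall", a verbal paired-associates test and the Memory Functioning Questionnaire.

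**The concern.** The posttest-only outcomes have no pretest of their own, so an analysis of change is not available for them. A covariate related to cognitive ability is the only way to take stable differences between people out of the error term. The plan has such scores at no extra cost and does not say that it will use them.

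The SAP declines any multiplicity adjustment because it does not want to give up power, and the planned power has no margin. If a baseline score predicts everyday memory even moderately, a plain t-test leaves some precision unused on the outcomes that matter most to the first hypothesis. The entry threshold sets a floor for TICS; it does not balance scores above that floor. With about 30 per arm, some chance difference in entry cognition is to be expected.

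**Working it through.** **Inputs from the documents.** n = 30 per arm, d = 0.64, one-tailed alpha .05, power .80 (SAP, Study 2). The covariate-outcome correlation within arm, R, is not given. It is an assumption, shown as a range.

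**Step 1: reproduce the stated power.** For an unadjusted t-test, df = 58 and the noncentrality is d × √(n/2) = 0.64 × √15 = 2.479. The one-tailed critical t is 1.672. Power is .790 by the noncentral t and .798 by the normal approximation. The detectable d at 80% power is 0.650. The stated .80 is essentially right.

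**Step 2: add k baseline covariates.** df = 58 − k, and the noncentrality becomes

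d × √15 / √[(1 − R²)(1 + k/(57 − k))].

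The last factor is the expected cost of estimating the covariate effects: 1 + 1/56 for one covariate, 1 + 2/55 for two. Example for k = 2, R = .4: 2.479 / √(0.84 × 1.0364) = 2.657 on 56 df, which gives power .836.

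| R (assumed) | Power, one covariate | Power, two covariates | Detectable d, two covariates |
|---|---|---|---|
| 0 | .783 | .776 | 0.66 |
| .2 | .798 | .791 | 0.648 |
| .3 | .816 | .810 | 0.631 |
| .4 | .842 | .836 | 0.606 |
| .5 | .877 | .871 | 0.573 |

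Unadjusted, for comparison: power .790, detectable d 0.650. Solving for equal power gives a break-even of about r = .13 with one covariate and R = .19 with two.

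**Step 3: effect of the TICS threshold.** Excluding low scorers narrows the TICS range and weakens its correlation with any outcome. The share excluded is not stated, so this is illustration only. If the cut removes the lowest 25% of a normal distribution, an unrestricted r of .3 becomes about .22 and .5 becomes about .39. If it removes 50%, they become about .19 and .33. At r = .22, TICS alone gives power of about .80, a gain of about one point.

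**Step 4: chance imbalance.** The standardised difference between arms in a baseline score has SE √(2/30) = 0.258. It exceeds 0.3 SD in one or other direction in about 25% of allocations, and in favour of EMMI in about 12%. Given an imbalance of size b, the one-tailed false-positive rate of the unadjusted test is approximately 1 − Φ[(1.645 − r·b/0.258)/√(1 − r²)].

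| Imbalance | r = .3 | r = .5 |
|---|---|---|
| 0.3 SD favouring EMMI | .087 | .110 |
| 0.3 SD against EMMI | .018 | .005 |

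Over all allocations these rates average to .05.

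**The case against.** The strongest reply is that no error has been shown. A two-sample t-test after randomisation is valid, and the design essentially meets its own power target without covariates. That stands, and it limits the point to an improvement.

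A reader might infer more in three ways, none of which the documents support:

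- **That the plan loses power.** This depends on a correlation the documents do not give. Two covariates gain nothing to speak of at R = .2 and lose slightly below about .19. Only R of .4 or more brings a gain of four points or better.
- **That chance imbalance undermines the test.** The unconditional type I error stays at .05, and the cost of imbalance is already in the standard error and in the reproduced power. It is not a second loss on top of noise. Quoting .09 to .11 alone shows one tail; the mirror case is .018 to .005. What adjustment does is remove the conditional effect of imbalance in the chosen covariates, in either direction. Nor is imbalance undetectable, because TICS and the pretest battery can be compared by arm.
- **That TICS was deliberately discarded.** The documents do not describe how randomisation was done. One can say only that no further use of TICS is stated.

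Other limits also stand. The choice of Word List Free Recall over another pretest measure is a judgement. Pretest scores precede training but follow assignment. Successful calls are out of four and memory slips are counts, so normal-theory gains are less predictable for them. The figures treat participants as independent although training is given in groups of 3 to 6, so differences of a point or two should not be pressed.

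**Conclusion.** The point holds as a low-cost efficiency improvement of uncertain size, not as the correction of an error. The posttest-only tests name no covariate, while pre-training scores that could serve are already collected. Under the assumed R of .2 to .5, two covariates change power at d = 0.64 from .790 to between .791 and .871. The loss at R = 0 is about .01. These figures rest on 30 analysed per arm, approximately normal outcomes, independent participants and an assumed R. TICS alone is likely to sit towards the lower end of the range because of the entry threshold, which is the reason to pair it with a pretest memory score.

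**What to change.** In the SAP paragraph on posttest-only analyses, make the primary analysis of each outcome a linear model of the outcome on arm, continuous screening TICS and one named pretest memory score, for example Word List Free Recall. Test the arm coefficient one-tailed in the direction already stated for that outcome. If only a strictly pre-randomisation covariate is wanted, use TICS alone, after confirming that screening preceded assignment.

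Also state that:

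- the covariates are fixed before outcomes are compared by arm. The documents describe administration and some data loss in the past tense, so the date of this decision should be recorded; if outcomes have already been compared by arm, the adjusted model should be labelled post hoc;
- participants with a missing pretest score are kept by simple baseline imputation, such as the mean pooled over both arms;
- the unadjusted t-test is reported as a sensitivity analysis.

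The cost is SAP wording and one or two degrees of freedom, with no new data. The downside is about .01 of power if the covariates prove unrelated to outcome, and a less predictable gain for calls out of four and memory slips.
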